5.3.2. MK-3475

MK-3475 will be administered IV, q3wks on Day 1 of each cycle, 30 minutes after completion of the PF-05082566 infusion and after the post-PF-05082566 and/or pre-MK-3475 pharmacokinetic blood samples are drawn.

MK-3475 will be administered as a 30 minute IV infusion. Sites should make every effort to target infusion timing to be as close to 30 minutes as possible. The exact duration of infusion should be recorded in both source document and CRFs. The infusion rate should be reduced or interrupted in the case of symptoms of infusion reaction, and symptomatic treatment administered. The infusion may be continued at one-half the previous rate upon improvement of symptoms. If symptoms persist or worsen, the infusion should be discontinued.

5.3.3. Treatment Duration

The study begins when the first patient signs the informed consent.

The treatment duration with both study drugs is 32 cycles (approximately 24 months) calculated from the date of the first combined doses of PF-05082566 and MK-3475. Patients may continue on treatment with both agents until disease progression (RECIST v. 1.1),

patient refusal, unacceptable toxicity occurs, or the study is prematurely terminated by the Sponsor; whichever comes first (see [Section 6.3](#) for Patient Withdrawal).

Discontinuation from treatment may be considered at the investigator's discretion for patients who have attained a confirmed CR, that have been treated for at least 24 weeks on study, and have at least two treatments with MK-3475 and PF-05082566 beyond the date the initial CR was declared. Patients who then experience radiologic disease progression will be eligible for re-treatment with both study drugs at the discretion of the investigator and by the approval of the Sponsor, if no cancer treatment was administered since the last dose of study drugs, the patient meets the safety parameters listed in the Inclusion/Exclusion criteria, and the trial is still open. Patients will resume therapy at the same dose and schedule at the time of initial discontinuation.

Patients who complete a maximum number of 32 cycles (approximately 24 months) on study treatment and demonstrate clinical benefit with manageable toxicity and are willing to continue receiving the study treatment will be given the opportunity to continue treatment upon agreement between investigator and sponsor.

CCI

A large rectangular area of the document is redacted with a solid black box.

CCI

A large rectangular area of the document is redacted with a solid black box.A rectangular area of the document is redacted with a solid black box.

■ 

A line of text is partially redacted with a solid black box.

■ 

A line of text is partially redacted with a solid black box.

■ 

A line of text is partially redacted with a solid black box.

- CCI [REDACTED]

5.3.5. Recommended Dose Modifications

Every effort should be made to administer PF-05082566 and MK-3475 at the planned dose and on schedule.

In the event of significant toxicity dosing may be delayed and/or reduced as described below. In the event of multiple toxicities, dose modification should be based on the worst toxicity observed. Patients are to be instructed to notify Investigators at the first occurrence of any adverse symptom.

Patients who experience an AE meeting the definition of a DLT may be removed from treatment, based on the dose modification guidelines listed in [Section 5.3.7.1](#) and in consultation with the Sponsor.

Dose modifications may occur in two ways:

- Between cycles: next cycle administration may be delayed due to persisting toxicity when a new cycle is due to start;
- In the next cycle: dose reduction may be required in a subsequent cycle based on toxicity experienced in the previous cycle.

Investigators are encouraged to employ best supportive care according to local institutional clinical practices and according to the guidance for selected adverse events provided below.

Dose modifications will be reported in the CRF.

5.3.6. Dose Delays

Re-treatment following treatment interruption for treatment related toxicity or at the start of any new cycle may not occur until all of the following parameters have been met:

- ANC $\geq 1,000/\mu\text{L}$;
- Platelet count $\geq 75,000/\mu\text{L}$;

- Non-hematologic toxicities have returned to baseline or Grade ≤ 1 severity (or, at the investigator discretion, Grade ≤ 2 if not considered a safety risk for the patient).

If a treatment delay results from worsening of hematologic or biochemical parameters, the frequency of relevant blood tests should be increased as clinically indicated.

Withhold scheduled dose for liver function test (LFT) related AEs (including asymptomatic) Grade ≥ 3 until return to baseline or Grade ≤ 1 severity. In cases of potential liver injury, see [Section 8.6.2](#). In such cases, consultation with a hepatologist should be considered in the decision to initiate treatment with anti-inflammatory medications.

After all toxicities have recovered within the limits described above, treatment with PF-05082566 and MK-3475 can be resumed. Both study drugs should be delayed simultaneously. If non-hematologic toxicity does not resolve to Grade 1 (or Grade ≤ 2 if not considered a safety risk for the patient) within 9 weeks of last infusion, consider permanent discontinuation after consultation with the Sponsor. With investigator and Sponsor agreement, patients with a laboratory adverse event still at Grade 2 after 9 weeks may continue treatment in the trial only if asymptomatic and controlled. In addition, consider discontinuation for any severe or life-threatening event.

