5.3.7. Dose Reductions

After the first two cycles (the DLT evaluation period), dose reductions in PF-05082566 and/or MK-3475 may be required based on the worst toxicity experienced in the previous cycle (see [Table 8](#)).

No specific dose adjustments are recommended for Grade 1/2 treatment-related toxicity. However, investigators should always manage their patients according to their medical judgment based on the particular clinical circumstances.

Patients experiencing recurrent and intolerable Grade 2 non-hematologic toxicity may resume dosing, with specific dose modifications detailed in [Section 5.3.7.1](#), once recovery to \leq Grade 1 or baseline is achieved. For guidance on dosing following immune related toxicities, see [Section 5.3.7.2](#).

Patients requiring dose reductions in PF-05082566 may be decreased one dose level (see [Table 7](#)). Patients treated at 2 mg/kg MK-3475 may be dose reduced to 1mg/kg due to AEs possibly attributed to MK-3475 alone. Once a patient has a dose reduction in PF-05082566 or MK-3475 for a drug-related toxicity, the dose will not be re-escalated. Patients requiring more than one dose reduction will be withdrawn from treatment unless otherwise agreed between the investigator and the Sponsor.

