5.3.7.1. Study Drug Dose Modification Guidelines

[Table 7](#) below shows the PF-05082566 and MK-3475 doses available for this study. Suggested dose modification guidelines are presented in [Table 8](#) below. Both study drugs should be held for the listed toxicities with dose modifications as suggested. For information

on the management of immune-related adverse events (see [Section 5.3.7.2](#) below). Patients requiring dose reductions in PF-05082566 due to dose-limiting toxicities may have study drug doses decreased one dose level (see Table 7). MK-3475 may be dose-reduced to 1 mg/kg due to AEs which may be recurrent or intolerable (beyond the DLT evaluation period) and possibly related to MK-3475, rather than PF-05082566, based on emerging safety and tolerability data.

Table 7. Available Dose Levels

PF-05082566*	MK-3475
50 mg/kg	2 mg/kg
3.6 mg/kg	1 mg/kg
1.8 mg/kg	
0.9 mg/kg	
0.45 mg/kg	
0.20 mg/kg	

Table 8. Dose Modification Guidelines for Treatment Related Adverse Events

Toxicity	Grade	Hold Treatment (Both Drugs)	Criteria for Treatment Restart (Both Drugs)	Dose Modification (Both Drugs*)	Discontinue Patient (after consultation with Sponsor) (Both Drugs)
Hematologic Toxicity meeting any of the DLT criteria in Section 3.3	3	Yes	Resolved to Grade 1 or better	Decrease dose by one dose level (based on Table 1).	If toxicity does not resolve within 9 weeks of last infusion, consider permanent discontinuation after consultation with the sponsor.
	4	Yes	Resolved to Grade 1 or better	Decrease dose by one dose level (based on Table 1).	If toxicity does not resolve within 9 weeks of last infusion, consider permanent discontinuation after consultation with the sponsor.
Non-Hematologic toxicity (other than immune-related toxicities described in Section 5.3.7.2 , 5.3.7.3 , 5.3.7.4)	1 and 2 (if not recurrent/intolerable)	No	N/A	Continue at same dose level.	N/A
	2 (recurrent/intolerable)	Consider withholding	Resolved to Grade 1 or better	Continue at same dose level. (reference Section 5.3.7.3 for recommendations regarding pneumonitis and Section 5.3.7.1 for guidance on reduction of the MK-3475 dose.	If toxicity does not resolve to Grade 1 or better within 9 weeks of last infusion, consider permanent discontinuation after consultation with the sponsor.

Toxicity	Grade	Hold Treatment (Both Drugs)	Criteria for Treatment Restart (Both Drugs)	Dose Modification (Both Drugs*)	Discontinue Patient (after consultation with Sponsor) (Both Drugs)

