	3 (only of maximally treated)	Yes	Resolved to Grade 1 or baseline or, at the investigator discretion, to Grade ≤ 2 if not considered a safety risk for the patient. For laboratory AEs only: resolved to Grade 2 and asymptomatic. For LFTs: resolved to Grade 1 or baseline.	Decrease dose by one dose level (based on Table 1).	If toxicity does not resolve to Grade 1 or baseline (or, at the investigator discretion, to Grade ≤ 2 if not considered a safety risk for the patient) within 9 weeks of last infusion, consider permanent discontinuation after consultation with the sponsor (except as noted in Section 5.3.7.1 for laboratory AEs). Permanent discontinuation should be considered for any severe or life-threatening event.
	4	Yes	Hold treatment until toxicity resolves to Grade 1 or baseline. For laboratory AEs only: resolved to Grade 2 and asymptomatic. For LFTs: resolved to Grade 1 or baseline.	Decrease dose by one dose level (based on Table 1).	If toxicity does not resolve within 9 weeks of last infusion, consider permanent discontinuation after consultation with the sponsor. Permanent discontinuation should be considered for any severe or life-threatening event.
*PF-05082566 dose will be modified based on dose levels listed in Table 1 . For AEs which are possibly related only to MK-3475, the dose may be reduced as described in Section 5.3.7.1 . See Table 9 for dose modification guidelines and suggested supportive care for immune-related Adverse Events (irAEs)					
See Table 10 for dose modification guidelines and suggested supportive care in patients experiencing pneumonitis					
See Table 11 for dose modification guidelines and suggested supportive care in patients enterocolitis.					
See Table 12 for dose modification guidelines and suggested supportive care in patients experiencing infusion reactions.					

N/A: not applicable.

5.3.7.2. Supportive Care Guidelines for Immune-Related Events of Clinical Interest (irECI) and Immune-Related Adverse Events (irAEs)

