  - derived absolute count  $\geq 800/\text{mm}^3$
- Neutrophil count decreased
  - derived absolute count does not meet Grade 2-4 criteria, and
  - % value < % LLN value, and
  - derived absolute count  $\geq 1500/\text{mm}^3$

For **calcium**, CTCAE grading is based on Corrected Calcium and Ionized Calcium (CALCIO). Corrected Calcium is calculated from Albumin and Calcium as follows:

$$\text{Corrected calcium (mmol/L)} = \text{measured total Calcium (mmol/L)} + 0.02 (40 - \text{serum albumin [g/L]})$$

**Liver function tests:** Alanine aminotransferase (ALT), aspartate aminotransferase (AST), and total bilirubin (TBILI) are used to assess possible drug induced liver toxicity. The ratios of test result over upper limit of normal (ULN) will be calculated and classified for these three parameters during the on-treatment period.

Summary of liver function tests will include the following categories. The number and percentage of patients with each of the following during the on-treatment period will be summarized by treatment group:

- ALT  $\geq 3 \times \text{ULN}$ , ALT  $\geq 5 \times \text{ULN}$ , ALT  $\geq 10 \times \text{ULN}$ , ALT  $\geq 20 \times \text{ULN}$ .
- AST  $\geq 3 \times \text{ULN}$ , AST  $\geq 5 \times \text{ULN}$ , AST  $\geq 10 \times \text{ULN}$ , AST  $\geq 20 \times \text{ULN}$ .
- (ALT or AST)  $\geq 3 \times \text{ULN}$ , (ALT or AST)  $\geq 5 \times \text{ULN}$ , (ALT or AST)  $\geq 10 \times \text{ULN}$ , (ALT or AST)  $\geq 20 \times \text{ULN}$ .

- $TBILI \geq 2 \times ULN$ .
- Concurrent  $ALT \geq 3 \times ULN$  and  $TBILI \geq 2 \times ULN$ .
- Concurrent  $AST \geq 3 \times ULN$  and  $TBILI \geq 2 \times ULN$ .
- Concurrent  $(ALT \text{ or } AST) \geq 3 \times ULN$  and  $TBILI \geq 2 \times ULN$ .
- Concurrent  $(ALT \text{ or } AST) \geq 3 \times ULN$  and  $TBILI \geq 2 \times ULN$  and  $ALP > 2 \times ULN$ .
- Concurrent  $(ALT \text{ or } AST) \geq 3 \times ULN$  and  $TBILI \geq 2 \times ULN$  and  $(ALP \leq 2 \times ULN \text{ or missing})$ .

Concurrent measurements are those occurring on the same date.

Categories will be cumulative, ie, a patient with an elevation of  $AST \geq 10 \times ULN$  will also appear in the categories  $\geq 5 \times ULN$  and  $\geq 3 \times ULN$ . Liver function elevation and possible Hy's Law cases will be summarized using frequency counts and percentages.

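### Protocol section 5.3.6 and Table 8 set different criteria for restarting both drugs in three situations, and no text says which governs

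*Protocol*

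**What the plan says.** **Section 5.3.6 (Dose Delays)** applies to every interruption for related toxicity and to every new cycle: "Re-treatment following treatment interruption for treatment related toxicity or at the start of any new cycle may not occur until all of the following" conditions hold. The conditions are:

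- a neutrophil count of at least 1,000/µL;
- platelets of at least 75,000/µL;
- "Non-hematologic toxicities have returned to baseline or Grade" 1 or lower, with Grade 2 acceptable if the investigator judges that it poses no safety risk.

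Liver function events of Grade 3 or above have their own, tighter condition. The section then adds: "After all toxicities have recovered within the limits described above, treatment with PF-05082566 and MK-3475 can be resumed". If non-hematologic toxicity has not reached Grade 1, or an acceptable Grade 2, within 9 weeks of the last infusion, permanent discontinuation is to be considered.

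**Table 8 (section 5.3.7.1)** sets restart criteria by type and grade of toxicity:

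- For "Hematologic Toxicity meeting any of the DLT criteria in Section 3.3", Grades 3 and 4, the criterion is "Resolved to Grade 1 or better".
- For recurrent or intolerable Grade 2 non-hematologic toxicity, the criterion is the same, and the 9-week discontinuation trigger is also tied to Grade 1.
- For Grade 4 non-hematologic toxicity: "Hold treatment until toxicity resolves to Grade 1 or baseline". Grade 2 is accepted only for laboratory events without symptoms, and not for liver function tests.

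**Section 5.3.7** also covers the recurrent Grade 2 case: "Patients experiencing recurrent and intolerable Grade 2 non-hematologic toxicity may resume dosing, with specific dose modifications detailed in" section 5.3.7.1. It makes this conditional on recovery to Grade 1 or to baseline.

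**The concern.** Both passages are current text, and both cover restart of the two drugs together after toxicity judged related to treatment. Where they disagree, one site may re-dose a patient whom another site would hold, and each can point to a protocol passage in support. The situations include recovery from DLT-type hematologic toxicity and from Grade 4 events, where a clear re-exposure rule matters most.

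The analysis is touched as well. SAP section 6.5.2.2 identifies reportable deviations from criteria in the protocol, and here those criteria differ. The length of a hold also feeds the dose-delay categories (SAP 6.5.3.4) and relative dose intensity (SAP 6.5.3.1 and 6.5.3.2). In one situation it could also decide whether a patient counts as a DLT, because failing to receive both infusions of each drug within the 6-week window is itself a DLT criterion (protocol section 3.3, SAP section 3.1).

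**Working it through.** The protocol gives no figure to reproduce, so the check sets the criteria side by side.

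| Situation | Section 5.3.6 | Table 8 | Patient in the gap |
|---|---|---|---|
| 1. After hematologic toxicity of DLT type | Neutrophils at least 1,000/µL | Grade 1 or lower | Grade 4 neutropenia recovered to 1,200/µL: neutrophil condition met under 5.3.6, held under Table 8 |
| 2. After a Grade 4 non-hematologic event that is neither a laboratory event nor covered by 5.3.7.2 to 5.3.7.4 | Baseline or Grade 1; Grade 2 by investigator judgement | Grade 1 or baseline | Recovered to Grade 2, judged no safety risk, baseline below Grade 2: may restart under 5.3.6, held under Table 8 |
| 3. Recurrent or intolerable Grade 2 non-hematologic toxicity that has been withheld | Baseline or Grade 1; Grade 2 by investigator judgement | Grade 1 | Still Grade 2, judged no safety risk: may restart under 5.3.6, held under Table 8 |

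**Width of the neutrophil gap.** Section 5.3.6 uses a count and Table 8 a grade, so a conversion is needed. The documents' only Grade 1 boundary for "Neutrophil count decreased" is in SAP section 6.6.5.1: a derived count of at least 1,500/mm³. Since 1 mm³ = 1 µL, the gap runs from 1,000/µL to just below 1,500/µL, and 1,500 − 1,000 = 500/µL. The SAP line is a reporting rule for differentials without an absolute reference range. Using it as the boundary that sites apply is an assumption.

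**Situation 3 in section 5.3.7.** That section sides with Table 8 in requiring Grade 1, but adds return to baseline as an alternative. The 9-week discontinuation trigger splits the same way: Grade 1 in Table 8, Grade 1 or an acceptable Grade 2 in 5.3.6.

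**Where the passages do not conflict.**

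- Grade 3 non-hematologic toxicity: Table 8 carries the same Grade 2 discretion as 5.3.6.
- Grade 4 laboratory events other than liver function tests, improved to Grade 2 without symptoms: both can permit restart.
- Liver function events of Grade 3 or 4: both require Grade 1 or baseline.
- Platelets: no comparison is possible, because the documents give no platelet boundary for Grade 1.

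**Reach into the primary endpoint.** Situation 1 concerns events that meet DLT criteria by definition. Situation 2 concerns Grade 4 non-laboratory events, and section 3.3 counts attributable Grade 3 or higher non-laboratory toxicity as a DLT. If such events occur in the window and are attributable, they are normally DLTs already, so restart timing does not change their status. That leaves situation 3. The window is 6 × 7 = 42 days and the second infusion is due on Day 1 + 21 = Day 22. The rules would separate a DLT from a non-DLT only if the investigator chose to withhold at Day 22 and the toxicity stayed at Grade 2 through Day 42. Restart at Grade 2 under 5.3.6 could complete the two infusions; a hold under Table 8 would not.

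**The case against.** The best defence is that 5.3.6 is a general minimum and Table 8 adds guidance for particular events. Section 5.3.6 is worded as a bar on earlier treatment, Table 8 is introduced as suggested guidance, and Table 8 is the stricter of the two in all three situations. A site that follows Table 8 therefore also satisfies 5.3.6. The last step is correct. The defence still fails as a reading of the text, because 5.3.6 makes its own limits sufficient as well as necessary: "After all toxicities have recovered within the limits described above, treatment with PF-05082566 and MK-3475 can be resumed". The paragraph introducing Table 8 also says that both drugs should be held for the toxicities listed, so the table is not plainly optional. No sentence ranks the two.

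The defence is right about scope. Four stronger readings are tempting, and the documents do not support them:

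- *Section 5.3.6 allows Grade 2 after any non-hematologic toxicity.* It does not. Liver function events of Grade 3 or above are excepted, the allowance depends on the investigator's safety judgement, and the section advises considering discontinuation after severe or life-threatening events. Immune-related toxicities have separate rules in 5.3.7.2 to 5.3.7.4.
- *Table 8 bars every patient with neutrophils between 1,000 and 1,500/µL.* Its only hematologic rows concern toxicity that meets DLT criteria.
- *Section 5.3.7 and Table 8 contradict each other on dose after recurrent Grade 2 toxicity.* The Table 8 cell that keeps the dose level goes on to cite 5.3.7.1 for MK-3475 reduction, and 5.3.7 cites the same section. They can be read together.
- *The conflict would shift the TITE-CRM estimate by a known amount.* One extra DLT can move a small posterior, but that shows the model's sensitivity to any single DLT under assumed data. In the only relevant situation, Table 8 asks the investigator just to consider withholding.

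**Conclusion.** The contradiction is real and narrow. In three defined situations 5.3.6 permits restart of both drugs where Table 8 holds them, and nothing in the protocol settles which applies. This much rests on the text alone.

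The size is a 500/µL neutrophil band in situation 1, if sites grade as the SAP reports, and the difference between recovery to Grade 2 and recovery to Grade 1 in situations 2 and 3. The documents give no basis for estimating how many patients would fall into these gaps. The main consequence is inconsistent re-exposure across sites after toxicity, with a secondary effect on deviation reporting and exposure summaries. A primary-endpoint effect is possible only in situation 3, needs several conditions to coincide, and is left unquantified. The correction is worth making because it concerns a safety rule and needs only wording.

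**What to change.** Reconcile sections 5.3.6 and 5.3.7 and Table 8 in a protocol amendment so that each toxicity type and grade has a single restart criterion, preferably in one place to which the others refer. Alternatively, state which passage governs where they differ. In the same amendment:

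- express the hematologic criterion on one scale, either a count or a CTCAE grade;
- make the treatment of return to baseline the same in 5.3.7 and in the recurrent Grade 2 row of Table 8;
- align the 9-week discontinuation trigger for that row with 5.3.6.

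Which threshold applies is for the sponsor's clinicians, and this review takes no view on it. The cost is amendment wording and notice to sites, with no added patients, visits or data collection.

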5.3.7. Dose Reductions

After the first two cycles (the DLT evaluation period), dose reductions in PF-05082566 and/or MK-3475 may be required based on the worst toxicity experienced in the previous cycle (see [Table 8](#)).

No specific dose adjustments are recommended for Grade 1/2 treatment-related toxicity. However, investigators should always manage their patients according to their medical judgment based on the particular clinical circumstances.

Patients experiencing recurrent and intolerable Grade 2 non-hematologic toxicity may resume dosing, with specific dose modifications detailed in [Section 5.3.7.1](#), once recovery to \leq Grade 1 or baseline is achieved. For guidance on dosing following immune related toxicities, see [Section 5.3.7.2](#).

Patients requiring dose reductions in PF-05082566 may be decreased one dose level (see [Table 7](#)). Patients treated at 2 mg/kg MK-3475 may be dose reduced to 1mg/kg due to AEs possibly attributed to MK-3475 alone. Once a patient has a dose reduction in PF-05082566 or MK-3475 for a drug-related toxicity, the dose will not be re-escalated. Patients requiring more than one dose reduction will be withdrawn from treatment unless otherwise agreed between the investigator and the Sponsor.

